4. OBJECTIVES AND ENDPOINTS

Objective	Endpoint
Co-Primary	
1. To determine the impact of thermal injury on the magnitude of small intestinal permeability change as soon as possible following injury compared to healthy participants	
 Lactulose/Mannitol (L/M) ratio at entry
2. To characterise the effect of thermal injury on small intestinal permeability over time and establish the clinical and demographic factors which can influence it	
 Changes in L/M ratio over time
Exploratory	
1. To determine the impact of thermal injury on colonic permeability as soon as possible following injury compared to healthy participants	
 Fractional excretion of sucralose at entry
2. To characterise the effect of thermal injury on colonic permeability over time	
 Changes in the fractional excretion of sucralose over time

Objective	Endpoint
3. To assess the relationship between severity of a participant's condition following thermal injury and changes in intestinal permeability†	
 • Number of ventilator-free days • Number of vasopressor-free days • Number of hemofiltration-free days • Number of episodes of confirmed infection and sepsis • Number of surgical interventions • Total length of hospital stay • Calculate critical care and thermal injury severity scores
4. To assess plasma and urine biomarkers of intestinal permeability, bacterial translocation and renal tubular dysfunction following thermal injury†	
 • Change in markers of intestinal mucosal damage samples from blood • Change in urine protein:creatinine and urine albumin:creatinine ratios
5. To assess the impact of thermal injury and intestinal permeability on the intestinal microbiome compared to healthy participants	
 • Changes in microbiome of acute and convalescent stool samples
6. To assess the impact of pre-existing co-morbid conditions on intestinal permeability and clinical outcome following thermal injury†	
 • Medical history and drug history at the time of admission
7. To assess wound healing	
 • Time to wound recovery (e.g. 95%)

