6.5. Exclusion Criteria for Thermal Injury Participants (Group 2)

Thermal injury participants are excluded from the study if any of the following criteria apply:

Medical Conditions

1. Chemical or electrical burn.
2. Multiple traumatic injuries with an Injury Severity Score (ISS) ≥ 16 (note: excludes burn in score system).

Prior/Concomitant Therapy

3. Patient received substantial undocumented management prior to arrival at the study site (burn centre) e.g. from paramedics or in a local accident and emergency department.
4. Systemic corticosteroid use.
5. Intravenous (IV) mannitol use.

Prior/Concurrent Conditions

6. Human immunodeficiency virus (HIV) infection.
7. Viral Hepatitis B or C infection.
8. Gastrointestinal disease (e.g. inflammatory bowel disease) which may affect intestinal permeability.
9. Previous bowel resection (e.g. hemicolectomy, small bowel resection)
10. Galatosaemia or severe lactose intolerance.
11. Bowel obstruction.
12. Renal dysfunction requiring renal replacement therapy (i.e. end-stage renal failure prior to thermal injury).
13. Active autoimmune disease and receiving immunomodulatory therapy e.g. rheumatoid arthritis anti-TNF.
14. Active chemotherapy for cancers or immunoremittive therapies (prednisolone, adalimumab) within 60 days of thermal injury.
15. Premorbid conditions of malignancy currently under treatment.
16. Previous bilateral lower extremity amputation.

NOTE: Due to the rapid recruitment period (within 24 hours of admission) for thermally injured participants, HIV and viral Hepatitis test results may not be available at the time of enrolment. In the event these tests return positive, the participant will be informed of the result(s) and withdrawn from the study (see Section 8.2.1). In the event that the participant has been recruited who lacked mental capacity to consent, the reason for their withdrawal (the positive HIV and/or viral Hepatitis test results) must not be shared with a personal consultee. According to UK law and the guidance of the British HIV association, if the participant's physician believes there is an overriding public interest to disclose the participant's results to a personal consultee who is a current or former sexual partner, then the result(s) may be disclosed without the participant's consent. This must be as a last resort. If the participant regains capacity, he/she will be informed of the positive test result(s).

Diagnostic assessments

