8.2.1. Other Withdrawal Criteria

- A participant will be withdrawn from the study following positive (and confirmed) HIV test at screening; Serologic evidence of active Hepatitis B (HB) infection based on the results of testing for HBsAg, and anti-HBc or a positive test for Hepatitis C antibody confirmed by Hepatitis C RNA or antigen testing. If HCV RNA is not available, then the positive test for Hepatitis C antibody alone would be exclusionary. Results must be discussed with the medical monitor to withdraw the participant from the study and commence therapy according to local practice.
- Healthy participants that are treated with antibiotics during the duration of the study.
- Participants that experience signs and symptoms of gastro-intestinal infections during the duration of the study.
- Withdrawals related to mental capacity as described in Section 6 and [Appendix 3](#).
- Participants that received haemodialysis during the first 48 hours of the study (i.e. during the first measurement of intestinal permeability) will be excluded from the evaluable population and a replacement will be recruited.
- Participants that received haemodialysis during later time points will not be excluded, but consideration will be given to recruiting an additional participant if 3 or more intestinal permeability measurements occur concurrently with haemodialysis.

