9.5.3. Other Clinical Responses

To assess the relationship between severity of a participant's condition following thermal injury and changes in intestinal permeability the following will be recorded and collected as a part of the SIFTI-2 study. Details can be found in the SIFTI-2 study protocol.

- Number of ventilator-free days (ventilator start/restart/end date/time)
- Number of vasopressor-free days (medication chart review)
- Number of hemofiltration-free days (notes review)
- Number of episodes of confirmed infection and sepsis
- Number of surgical interventions
- Total length of hospital stay
- Calculate critical care and thermal injury severity scores

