	Clostridium difficile infection/pseudomembranous colitis	
Renal/Urology problems	Acute rhabdomyolysis	Record AE
	Acute renal failure	Ensure biochemistry and CK results recorded n CRF
	Acute urinary retention	
	Renal replacement therapy	

System Assessment	Complication type	Action
Thromboembolic complications	Lower limb DVT	Record AE with location of thrombus
	Upper limb DVT	
	Pulmonary embolism	
	Other VTE	
	Fat embolism	
Wound complications	Major graft loss	Record AE with details
	Major skin substitute loss	
	Wound infection	
	Invasive wound infection	

Definition of SAE

If an event is not an AE per definition above, then it cannot be an SAE even if serious conditions are met (e.g., hospitalization for signs/symptoms of the disease under study, death due to progression of disease).

Please note that, as described in Section 9.2.6 a, b, c and d below are considered as 'disease related events' as they occur commonly in patients following thermal injury unless, in the opinion of the investigator, they are directly related to STM administration or other unique requirements of the HESTIA study.

A SAE is defined as any untoward medical occurrence that:

a. Results in death

b. Is life-threatening

The term 'life-threatening' in the definition of 'serious' refers to an event in which the participant was at risk of death at the time of the event. It does not refer to an event, which hypothetically might have caused death, if it were more severe.

c. Requires inpatient hospitalization or prolongation of existing hospitalization

In general, hospitalization signifies that the participant has been detained (usually involving at least an overnight stay) at the hospital or emergency ward for observation and/or treatment that would not have been appropriate in the physician's office or outpatient setting. Complications that occur during hospitalization are AE. If a complication prolongs hospitalization or fulfils any other serious criteria, the event is serious. When in doubt as to whether "hospitalization" occurred or was necessary, the AE

should be considered serious.

Hospitalization for elective treatment of a pre-existing condition that did not worsen from baseline is not considered an AE.

d. Results in persistent disability/incapacity

- The term disability means a substantial disruption of a person's ability to conduct normal life functions.

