3. ANALYSIS POPULATIONS

Population	Definition / Criteria	Analyses Evaluated
Screened	All participants who were screened for eligibility	Study PopulationAll Listings
Safety	Comprise of all participants who receive at least one dose of STM and have at least one post-dose safety assessment.	Safety
Evaluable	Comprises of all participants in the safety population excluding any healthy volunteers that received any concomitant medication or food and drink containing STM (lactulose, mannitol and sucralose), as identified by review of the protocol deviations.	EfficacyBiomarkerStudy Population

NOTES:

 Please refer to Appendix 8: List of Data Displays which details the population to be used for each display being generated.

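### The SAP's Evaluable Population omits the protocol's renal replacement exclusion for thermal injury participants, and the protocol rule itself names haemodialysis but not haemofiltration

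*Protocol*

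**What the plan says.** Protocol section 8.2.1 (current text, Amendment 2) has a rule for "Participants that received haemodialysis during the first 48 hours of the study", a window that it equates with the first permeability test. Such participants are left out of the evaluable set and replaced. Participants treated at later time points stay in, and an extra recruit is considered "if 3 or more intestinal permeability measurements occur concurrently with haemodialysis". Haemofiltration appears in neither bullet.

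Elsewhere the protocol expects these patients to need renal support. Section 4 has "Number of hemofiltration-free days" as an exploratory endpoint, and section 9.5.3 collects it by notes review through SIFTI-2. Appendix 4, Table 3 lists "Renal replacement therapy" among the complications of severe burns. The entry exclusion in section 6.5 covers only "Renal dysfunction requiring renal replacement therapy (i.e. end-stage renal failure prior to thermal injury"), so support started after the burn does not bar entry. Section 10.4 requires evaluable L/M measurements for the Evaluable Population but does not say what makes one evaluable.

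SAP section 3 defines the same population in these words: "Comprises of all participants in the safety population excluding any healthy volunteers that received any concomitant medication or food and drink containing STM", as identified by review of the protocol deviations. Nothing is excluded on the thermal injury side. SAP section 6.1.3 uses this population for the primary analyses, and section 4.2 makes Day 1 the baseline in both groups. SAP Table 1, which sets out changes from the protocol analysis, does not mention the renal rule.

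**The concern.** The protocol takes a participant out of the evaluable population, and the SAP, citing that same protocol version, leaves the participant in. A programmer following the SAP would produce a different primary analysis set from the one the protocol promises, with no recorded reason.

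The haemodialysis-only wording adds a second gap. If the rule exists because a blood circuit can take up sugar that would otherwise reach the urine, the reason does not depend on which circuit is used. Restoring 8.2.1 word for word in the SAP would still leave a participant on haemofiltration at the first test in the set.

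At stake are the L/M ratio at entry (co-primary 1), the Day 1 baseline under every change and percentage change (co-primary 2), and the exploratory fractional excretion of sucralose.

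**Working it through.** **1. Analysis set, side by side.**

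| Participant at first test | Protocol 8.2.1 | SAP section 3 |
|---|---|---|
| On haemodialysis | Excluded and replaced | Retained |
| On haemofiltration | Not named | Retained |

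No other SAP rule removes such a participant. Section 3 uses the deviation review only to exclude healthy volunteers, and needing renal support is not a deviation. Section 10.6.1 keeps the available planned data of withdrawn participants in tables and figures unless otherwise specified.

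**2. Reason for the rule.** The amendment history, used here only as evidence of intent, says renal replacement therapy, glossed as dialysis, may filter out lactulose and mannitol. That reason covers haemofiltration as well.

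**3. How removal would act.** SAP section 10.5.2 sets FE = urine concentration × urine volume / dose, and L/M = FE lactulose / FE mannitol. Let u be the fraction of each absorbed sugar that still reaches the urine.
- Measured L/M = true L/M × (u_L / u_M). Write f = u_L / u_M. Equal losses cancel (f = 1); unequal losses do not.
- Measured sucralose FE = true FE × u_S. Nothing cancels. This assumes sucralose is removed too; the stated reason names only the other two sugars.

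The documents give no value for any u, so the size and direction of f are unknown. I take f from 1/3 to 3 as an assumed range.

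**4. The plan's own figure first.** Protocol section 10.2: 25 against 15, 3-fold ratio, log SD 1.15, two-sided 0.10, stated power 89%.
- SE = 1.15 × √(1/25 + 1/15) = 0.3756; ln 3 / SE = 1.0986 / 0.3756 = 2.925.
- Normal approximation: Φ(2.925 − 1.645) = 0.900. Noncentral t with 38 df: 0.890. The stated figure reproduces (natural logs) and is not in dispute.

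**5. Planned size, k of 25 affected and retained.** Expected ratio = 3 × f^(k/25). For power, the thermal injury variance is 1.15² + q(1 − q)(ln f)² with q = k/25 (normal approximation, reference 0.900).

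| k | Ratio, f = 1/3 to 3 | Power |
|---|---|---|
| 1 | 2.87 to 3.13 | 0.87 to 0.92 |
| 3 | 2.63 to 3.42 | 0.81 to 0.94 |

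Excluding one of 25 without replacement gives 88.6% by the t calculation.

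**6. Actual size, one of 3 affected.**
- Geometric mean multiplied by f^(1/3): 0.69 to 1.44.
- The SAP reports arithmetic means. If the three true values were equal, the mean is multiplied by (2 + f)/3: 0.78 to 1.67.
- Percentage change from an affected baseline is 100 × (r/f − 1), where r is the true later-to-entry ratio. With no true change (r = 1), f = 1/3 shows +200% and f = 3 shows −67%.

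**The case against.** The strongest reply has five parts.

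- **Loose wording.** The amendment history uses renal replacement therapy, dialysis and haemodialysis for the same change, so haemodialysis may be shorthand for all of them. This is plausible. A reader might infer that the sponsor chose to keep haemofiltration participants in; the documents do not support that. It remains a reason to write the scope down.
- **The protocol may already deal with it.** Section 10.4 admits only evaluable L/M measurements, so a compromised first test could be set aside. That stands for the protocol, although no criterion is given. The SAP definition drops this condition.
- **Not shown to be invalid.** A reader might infer that L/M values obtained during filtration are invalid. The recorded reason says only that sugars may be filtered, section 3.2.2 presents mannitol as normalising lactulose for factors that include renal function, and 8.2.1 itself retains later tests done during haemodialysis. This objection stands for L/M: potentially unreliable is as far as the text goes. Sucralose FE has no such offset.
- **Little left to bias.** The study stopped with 3 thermal injury participants, the SAP makes no formal comparison, and the replacement and three-test rules can no longer operate. This also stands: the effect falls on descriptive tables and plots.
- **Partly visible already.** Renal replacement therapy can appear as a disease-related event (SAP Table 3.3, Listing 17), hemofiltration-free days may be described in the study report where relevant, and each participant is plotted. But no L/M or sucralose display links a given test to renal support.

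**Conclusion.** The point holds as a contradiction between the two documents over who is in the primary analysis set, together with a protocol rule narrower than its own reason. Under the SAP as written, a thermal injury participant on haemodialysis at the first test stays in, although the protocol says the opposite; one on haemofiltration stays in as well, and the protocol is silent.

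The size depends on facts the documents do not give. Each affected participant is 1/25 = 4% of the planned group and 1/3 of the actual group. The shifts in the working rest wholly on the assumed range for f; at f = 1 there is none in L/M. A reader might infer that the reported entry values are in fact distorted. That is not supported: no document says that any of the 3 received renal replacement therapy, and no rate in the first 48 hours is given. With three participants and descriptive reporting, this is a correction to make before the summaries are read, and it does not by itself undermine the study.

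**What to change.** 1. In SAP section 3, add to the Evaluable Population the exclusion of thermal injury participants who received renal replacement therapy (haemodialysis or haemofiltration) during the first permeability measurement, which 8.2.1 equates with the first 48 hours. If the sponsor prefers to retain them, list that in SAP Table 1 with the reason.
2. Align 8.2.1 with this by naming the modalities in both bullets. If amending the protocol of a terminated study is not worthwhile, one sentence in the SAP stating how 8.2.1 is read would serve.
3. In Listing 24 and the thermal injury plots of L/M and sucralose, flag later tests done during renal replacement therapy, and keep those values in as 8.2.1 provides.

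This changes an analysis-set definition and leaves patient care untouched. It costs one line in the SAP, a flag in existing displays that needs treatment dates matched to test dates, and ethics approval if the protocol text is amended (section 12.3.1). The real downside is possibly one fewer evaluable participant out of very few.

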10.4. Populations for Analyses

The **Safety Population** will consist of all subjects who receive at least 1 dose of STM and have at least on post-dose safety assessment.

The **Evaluable Population** will consist of all subjects who are entered into the study and have evaluable L/M ratio measurements.

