12.6. Appendix 6: Protocol Amendment History

The Protocol Amendment Summary of Changes Table for the current amendment is located directly before the Table of Contents (TOC).

Amendment 01 (15-Aug-2017)

Overall Rationale for the Amendment: The interim analysis has been removed since lactulose and mannitol data in healthy controls was unlikely to change the required sample size in thermally injured participants.

Section # and Name	Description of Change	Brief Rationale
10.5.3 Interim Analysis	Removed preliminary review of lactulose/mannitol ratio data.	Analysis of lactulose and mannitol data in healthy controls would be unlikely to change the study size, and will no longer be performed.
5.2 Number of Participants	Included withdrawn participants may be replaced.	To ensure the target number of evaluable population is maintained.
5.4.4 Preliminary Data Review	Modified the preliminary data review.	To describe the change in preliminary data review.
Synopsis	Updated preliminary data review.	For consistency.
6.5 Exclusion Criteria	Revision to eligibility criteria to exclude hepatitis infection for thermally injured participants. Addition the personal consultee will not be notified if a patient lacking mental capacity was found to be HIV positive.	Consistency correction. Hepatitis screening will be performed. To provide Ethic Committee reassurance and address any ambiguity of this information.
8.2.1 Other Withdraw Criteria	Added the withdraw of participants receiving hemodialysis.	Renal replacement therapy (i.e. dialysis) may filter out lactulose and mannitol.
9.2.2 Time Period and Frequency for Collecting AE and SAE Information	Added: Any SAEs assessed as related to study participation will be recorded from the time a participant consents. All SAEs will be recorded and reported to the sponsor or designee immediately and under no	To align with the updates to Clinical Protocol Template (Vol 7) effective 7th April 2017.

Section # and Name	Description of Change	Brief Rationale
	circumstance should this exceed 24 hours.	
9.4 Clinical Safety Laboratory Assessments	Removal of if laboratory values from non-protocol specified laboratory assessments performed at the institution's local laboratory.	To align with the updates to Clinical Protocol Template (Vol 7) effective 7th April 2017.

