6.1.4. Statistical Analyses / Methods

Endpoints defined in Section 6.1.1 will be summarised by study group, timepoint and visit. Data will summarise mean, standard deviation, standard error, minimum, median, maximum and N.

No formal statistical analysis will be performed.

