10.5. Appendix 5: Derived and Transformed Data

10.5.1. General

Multiple Measurements at One Analysis Time Point

- Mean of the measurements will be calculated and used in any derivation of summary statistics but if listed, all data will be presented.
- If there are two values within a time window the value closest to the target day for that window will be used. If values are the same distance from the target, then the mean will be taken.

Study Day

- Calculated as the number of days from First STM Dose Date:
 - Ref Date = Missing → Study Day = Missing
 - Ref Date < First STM Dose Date → Study Day = Ref Date First STM Dose Date
 - Ref Data ≥ First STM Dose Date → Study Day = Ref Date (First STM Dose Date) + 1

Age

Age = Screening date – Date of Birth
 Date of birth will be imputed based on the assumption that all subjects were born on the 30th June (30 Jun YYYY).

Baux score

Baux score: Age + % Total Body Surface Area (TBSA) burned

10.5.2. **Efficacy**

Fractional Excretion of Lactulose/Mannitol/Sucralose

Data is provided to S&P in the form of quantity of material in micrograms/litre, based on a sample of urine.

Fractional excretion (FE) of lactulose or mannitol or sucralose = (urine concentration (micrograms/litre) × total urine volume excreted in litre) / probe input (micrograms).

Where,

- Urine concentration is provided in the BIOMARKER dataset,
- Urine volumes excreted are provided in the BIOLINK dataset,
- Probe input refers to the total STM taken (as per Table 7.1 of the protocol-5g Lactulose, 2g Mannitol and 2g Sucralose)

Urine concentration in the BIOMARKER dataset will be provided at two timepoints per visit (0-5hr) and (0-24hr)

FE will be calculated for timepoints 0-5 and 0-24 hours for Lactulose, Mannitol and Sucralose.

For calculations of the 0-24 FE's, total urine volume will be based on the following:

Total urine=urine excreted 0-5 hrs + urine excreted 5-24 hours.

Note: If urine excreted 0-5 hrs is missing then total urine should be considered missing.

Note: 1g=1000000 micrograms

L/M ratio

L/M ratio = FE lactulose / FE mannitol

Healthy Participant – Average

• Average = Mean of all data available at all timepoint for each healthy participant.

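### Sugar tests run during later dialysis enter the L/M and sucralose time course unmarked, although the protocol's own dialysis rule rests on possible loss of the test sugars

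*Protocol*

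**What the plan says.** Protocol 8.2.1 has two haemodialysis rules. A participant dialysed in the first 48 hours, during the first permeability measurement, "will be excluded from the evaluable population and a replacement will be recruited". For dialysis after that: "Participants that received haemodialysis during later time points will not be excluded, but consideration will be given to recruiting an additional participant", and this only "if 3 or more intestinal permeability measurements occur concurrently with haemodialysis". The amendment history (Protocol 12.6) gives the reason for adding the rule: "Renal replacement therapy (i.e. dialysis) may filter out lactulose and mannitol".

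SAP 10.5.2 computes fractional excretion (FE) as urine concentration times "total urine volume excreted in litre) / probe input (micrograms"), and L/M as FE of lactulose over FE of mannitol. Nothing is added for sugar leaving by another route.

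The protocol's Evaluable Population (10.4) is "all subjects who are entered into the study and have evaluable L/M ratio measurements"; what makes a measurement evaluable is not defined. The SAP version (Section 3) reads: "Comprises of all participants in the safety population excluding any healthy volunteers that received any concomitant medication or food and drink containing STM". It mentions dialysis nowhere, at the first test or later.

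For L/M, SAP 6.1.4 states: "Endpoints defined in Section 6.1.1 will be summarised by study group, timepoint and visit". SAP 6.2 plans descriptive summaries of sucralose excretion, and Appendix 8 (Tables 2.1–2.6, Figures 2.1–2.8) gives absolute, change and percent-change displays for both measures.

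**The concern.** The protocol regards dialysis at the first test as serious enough to remove the participant from the evaluable population. The same test, measured the same way two days later, goes into the time course with no mark on it. Recruiting another participant does nothing to the affected value. A reader of the tables or individual plots could not tell a real change in permeability from sugar lost to the dialyser. The second co-primary endpoint, change in L/M over time, and the exploratory sucralose time course are the results exposed.

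The documents handle other threats to the same measurement test by test. Protocol 6.6.1 stops a test when a product containing a probe sugar cannot be avoided, Protocol 7.7 delays testing after intravenous mannitol, and SAP 10.5.2 sets total urine to missing when the 0–5 hour volume is missing. Dialysis has no counterpart.

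**Working it through.** **The plan's own figure.** Protocol 10.2 gives 89% power for a 3-fold difference in L/M with 25 and 15 participants, log-scale SD 1.15 and two-sided alpha 0.10. With difference ln 3, the noncentral t calculation gives 89.0% and the normal approximation 90.0%, so it reproduces. This point does not alter it: it is an illustration of the burn-versus-healthy difference, which the plan assesses at entry, and the concern here is with later tests.

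**How many tests can be affected.** The preferred schedule (Protocol 2.2) is Days 1, 3, 5, 7, 9, 11 and 13: seven tests, six after the first. SAP 1.3 says nobody reached Day 28, so these are the relevant ones. Up to 2 of 6 (33%) can coincide with dialysis before the protocol responds at all. At 3 of 6 (50%) the response is to consider one more recruit, and the values stay in.

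**Bias in one affected test.** Let f be the fraction of an absorbed sugar removed by dialysis, the rest reaching the urine as it otherwise would. Then:

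- observed FE = true FE × (1 − f)
- observed L/M = true L/M × (1 − fL)/(1 − fM)

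The documents give no value for f. The range 0 to 75% per sugar is an assumption.

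| fL | fM | Apparent change in L/M, true value unchanged |
|---|---|---|
| equal to fM | equal to fL | 0% |
| 0 | 25% | 1/0.75 − 1 = +33% |
| 25% | 50% | 0.75/0.50 − 1 = +50% |
| 50% | 25% | 0.50/0.75 − 1 = −33% |
| 0 | 50% | 1/0.50 − 1 = +100% |

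The extremes of the range are −75% (fL = 75%, fM = 0) and +300% (fL = 0, fM = 75%).

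Sucralose has no denominator sugar. If it is removed at all, FE falls by f: 10%, 25%, 50% or 75% removal reads as −10%, −25%, −50% or −75%.

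**Effect on a visit mean.** SAP 1.1 gives 3 thermally injured participants. With one dialysed and the other two unchanged, the mean percent change moves by a third of the individual bias:

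- sucralose, 50% removed: −50/3 = −17 percentage points
- L/M doubled: +100/3 = +33 points
- L/M at −33%: about −11 points

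In the individual plots the whole bias appears as one unmarked point.

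**First test.** Because the SAP population omits the 48-hour exclusion, a dialysed Day 1 test could serve as baseline. If half of one participant's sucralose were lost at baseline only, every later undialysed test would read 1/0.50 − 1 = +100% with nothing truly changed.

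**Whether anything else catches it.** SAP 10.4.2 deals with departures from planned times, not dialysis. SAP 10.6.1 brings available planned data from withdrawn participants into tables and figures. Haemofiltration-free days are collected in SIFTI-2 by notes review (Protocol 9.5.3), but SAP Table 1 does not analyse them and allows only description in the study report where relevant.

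**The case against.** Protocol 8.2.1 is a rule about participants, and keeping a participant dialysed later is reasonable. It does not say the affected values must be analysed. Protocol 10.4 speaks of evaluable measurements, and Protocol 10 leaves detailed methods to the reporting plan. This stands: the omission belongs mainly to the SAP, whose population definition dropped the one word that might have covered it.

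Protocol 3.2.2 presents mannitol as normalising lactulose for factors such as renal function, and the amendment history names both sugars as possibly filtered. If losses are proportional, L/M is unbiased. This also stands, but only under equal removal, which nothing in the documents establishes, and sucralose has no such protection.

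The SAP is descriptive, and listings and individual plots show every value. That limits the harm, but none of those displays marks dialysis.

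Some stronger readings are tempting and should be resisted. A reader might take the three-test trigger as an admission that such values are unusable; it commits only to considering another recruit, which fits caution or lost precision equally well. A reader might also say that the protocol expects sucralose to be filtered; it names lactulose and mannitol only. Finally, setting affected values to missing may look like the obvious remedy. With 3 participants it would remove data selectively from those ill enough to need dialysis, and the mean would shift according to who was left.

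**Conclusion.** The gap is real and modest. The plan acts on possible sugar loss at the first test and is silent on the same possibility at later tests, so tests coinciding with dialysis enter the time course unmarked.

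For L/M, bias arises only if the two sugars are removed in unequal proportions, and its direction is then unknown. The documents do not support saying that dialysis inflates L/M or that it mimics recovery in L/M. For sucralose the direction would be downward, resembling recovery, but removal of sucralose is inferred from the urinary-recovery method and the endpoint is exploratory. Every removal fraction used here is an assumption. The documents do not say whether any of the 3 burn participants was dialysed, so a reader should not infer that the reported results are affected. If one was, that participant's test carries at least a third of the weight in a visit mean.

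The SAP population's omission of the 48-hour exclusion is a plain inconsistency with Protocol 8.2.1, whatever the size of any bias.

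**What to change.** In SAP 10.5.2, define a flag for every test whose urine collection overlaps haemodialysis or other renal replacement therapy, derived from partner-study records. The wider wording is needed because Protocol 8.2.1 speaks of haemodialysis, the amendment history of renal replacement therapy, and Protocol 9.5.3 of haemofiltration. Mark flagged values in Listing 24 and in the thermal injury figures (2.2, 2.3 and 2.5–2.8), and present Tables 2.1–2.6 with and without flagged tests. No data are lost.

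Separately, reconcile the SAP Section 3 Evaluable population with the first-48-hour exclusion in Protocol 8.2.1, or state why they differ.

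The cost is one extra set of summaries and a check of dialysis dates. These may be recorded only by day, so the SAP should say how a same-day overlap is classified. If no participant was dialysed, one sentence saying so closes the time-course point.
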